### Modified Intention-to-Treat (ITT) population (Primary analyses)

Based on the data review performed before conducting the final analysis, we found that quite a few subjects in this pragmatic trial did not receive treatment according to their assigned group. In the ITT population, those patients who received treatment in the group opposite to the one to which they were randomized would also be included in the analysis. Based on the concern that these subjects could cause a potential bias toward the noninferiority claim with the ITT analysis, we have defined a modified ITT population. In order to be conservative with regard to testing the non-inferiority hypothesis, the primary analyses will rely on the modified ITT population. The modified ITT population includes all subjects who received a study drug according to their assigned treatment group and participated in this study.

The modified ITT population for the randomized cohort includes all randomized subjects who received at least one dose of the anti-coagulation treatment strategy to which they were assigned. The preference modified ITT population includes all non-randomized subjects who received the anti-coagulation treatment which they preferred subsequent to informed consent to study participation. The full modified ITT population includes the sum of the two aforementioned categories (randomized cohort and preference cohort).

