## 3.2. Definition of analysis populations

### Intention-to-Treat (ITT) population

The intention-to-treat population for the randomized cohort includes all randomized subjects. The corresponding population for the preference cohort consists of all patients who would not be randomized but participated in this study. The corresponding population for the full cohort consists of all randomized subjects and all subjects in the preference cohort. In the analyses with the ITT population, we performed the analyses by group, using the assigned treatment group indicator regardless of whether the subject received the assigned treatment or not.

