#### 3.5.2. Analysis for the primary endpoint

##### 3.5.2.1. Primary analysis

The primary aim of this study is to compare the intervention and comparator arms with respect to their ability to prevent recurrent VTE. Because the intervention (DOAC therapy) is more easily administered than the comparator (usual care with LMWH warfarin), DOAC is expected to have higher adherence and therefore decreased incidence of VTE. Accordingly, a noninferiority design with a superiority alternative is preferred, as described by Friedlen et al. The primary analysis will test the noninferiority of the DOAC therapy with the primary analytic cohort (modified ITT population of the randomized cohort). If noninferiority is demonstrated, superiority of the DOAC therapy will be tested.

Because VTE is often a proximate cause of death in cancer patients' unexplained sudden demise, but diagnostic procedures are rarely performed (post-mortem scans, autopsies, etc.), we considered VTEs that were clinically significant as the primary outcome on the basis of an antemortem diagnosis. Separately, we looked at all-cause deaths because deaths from cancer and deaths from VTE are difficult to distinguish. Cancer patients routinely die at home and it is not possible to determine whether the proximate cause of death was a VTE, progression of tumor or some other cause. Indeed, the cause of many deaths in cancer patients is multifactorial. We will estimate the cumulative incidence of recurrent VTE at 6 months using standard competing risk analysis methods, where death will be treated as a competing risk. We calculate the difference in the 6 months incidence rate between groups and the corresponding 0.90 confidence interval (CI).

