## 2) Superiority test of DOAC

If noninferiority of DOAC is demonstrated, a superiority test of DOAC will be performed using a one-sided 0.05 significance level and the same two-sided 90% CI for the difference in the event rate of the primary endpoint at 6 months as used for the noninferiority test. When the upper bound of the CI is less than 0, we will conclude that DOAC therapy is superior to LMWH/warfarin in terms of VTE prevention. Because we will perform the superiority test only after the noninferiority of DOAC is demonstrated, the overall type I error rate is maintained at the 0.05 level (one-sided) without splitting alpha.

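### Superiority is decided in the modified ITT set, which the SAP justifies only as conservative for noninferiority; ITT, the conservative set for superiority by the same reasoning, has no say in the claim

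*Combined protocol and SAP*

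**What the plan says.** SAP 3.2 explains where the mITT set came from: "Based on the data review performed before conducting the final analysis, we found that quite a few subjects in this pragmatic trial" were not treated in line with their allocation. It fears that "these subjects could cause a potential bias toward the noninferiority claim with the ITT analysis", and concludes: "In order to be conservative with regard to testing the non-inferiority hypothesis, the primary analyses will rely on the modified ITT population". For the randomised cohort the set is "all randomized subjects who received at least one dose of the anti-coagulation treatment strategy to which they were assigned". The ITT set keeps every randomised patient, "using the assigned treatment group indicator regardless of whether the subject received the assigned treatment or not".

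SAP 3.5.2.1 tests noninferiority in the mITT set of the randomised cohort and continues: "If noninferiority is demonstrated, superiority of the DOAC therapy will be tested". No other population is named for that second step. The superiority test uses "the same two-sided 90% CI for the difference in the event rate of the primary endpoint at 6 months as used" for noninferiority, and superiority is concluded when the upper bound is below 0. The sequential order is given as the reason why "the overall type I error rate is maintained at the 0.05 level (one-sided) without splitting alpha". Protocol 13.3.1 has the same rule.

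ITT appears as a sensitivity repeat of all the analyses (SAP 3.5.2.3 item 6; protocol 13.3.3 item 6; protocol 8.9). Nothing says what follows if ITT and mITT disagree on superiority. SAP 3.6.2 and protocol 13.3.5 carry the same noninferiority-then-superiority sequence over to major bleeding.

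**The concern.** The stated reason for mITT covers one of the two hypotheses it decides. If patients treated with the other arm's class push the ITT difference toward zero, that helps a noninferiority claim and hinders a superiority claim. The SAP's argument for leaving ITT when testing noninferiority is therefore an argument for using ITT when testing superiority. The documents do not draw this second conclusion; it follows from the first.

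Taking a dose of the assigned strategy is an event after randomisation in an unblinded trial (protocol 3.1). The reasons that the Treatment Status Update Form lists for not being on the assigned arm include insurance non-coverage, refusal and transfer of care (protocol 8.5). These could differ by arm and could be related to VTE risk. If both happen, the patients left in the two mITT arms are no longer comparable by design. A superiority claim could then reflect who was dropped, and the analysis that keeps everyone could not prevent it.

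**Working it through.** **Inputs from the documents.** 671 randomised (SAP 2.5), 1:1 (SAP 2.2), so 335.5 per arm. Final critical value 1.710, one-sided 0.0436 (SAP 3.5.2.2). Margin 3 points (SAP 3.5.2.1). Superiority power 0.756 with 668 randomised and 0.797 with 750 (SAP 2.5).

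**Assumed inputs.** The 6-month event rate r, the excluded share x in each arm, and the risk RR of excluded relative to kept patients. The documents give none of these.

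**1. The plan's own figures.** 1 − Φ(1.710) = 0.0436, and 1 − 2 × 0.0436 = 91.28%, both as stated. Scaling the 750 row to 668: Φ((0.831 + 1.645) × √(668/750) − 1.645) = 0.755, against 0.756 stated. The power itself cannot be rebuilt, because no design event rates are given.

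**2. False superiority in mITT, no drug effect.** All randomised patients have the same rate r in both arms. The rate among kept patients is k = r / ((1 − x) + x·RR), with 335.5(1 − x) kept per arm and an unpooled SE. False superiority = Φ(−1.710 − (k_DOAC − k_UC)/SE).

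Example: r = 8%, x = 20% usual care and 5% DOAC, RR = 0.5 in both arms. Then k_UC = 0.08/0.90 = 8.89% and k_DOAC = 0.08/0.975 = 8.21%. SE = 0.0232, the ratio is −0.295, and Φ(−1.415) = 0.0785.

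| Excluded, usual care / DOAC | RR | k_UC / k_DOAC | False superiority |
|---|---|---|---|
| 10% / 2% | 0.5 both arms | 8.42% / 8.08% | 0.0600 |
| 20% / 5% | 0.5 both arms | 8.89% / 8.21% | 0.0785 |
| 10% / 2% | 0.5 usual care only | 8.42% / 8.00% | 0.0645 |
| 20% / 5% | 0.5 usual care only | 8.89% / 8.00% | 0.0926 |
| 10% / 2% | 2 both arms | 7.27% / 7.84% | 0.0238 |
| 20% / 5% | 2 both arms | 6.67% / 7.62% | 0.0155 |
| 2% / 10% | 0.5 both arms | 8.08% / 8.42% | 0.0311 |
| 5% / 20% | 0.5 both arms | 8.21% / 8.89% | 0.0225 |
| 2% / 10% | 2 both arms | 7.84% / 7.27% | 0.0751 |
| 5% / 20% | 2 both arms | 7.62% / 6.67% | 0.1034 |
| any | 1 | 8.00% / 8.00% | 0.0436 |
| equal shares | equal | equal | 0.0436 |

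With r from 6% to 10% and the first two pairs of shares, half risk in both arms gives 0.057 to 0.084.

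**3. The same test in ITT.** The rates are equal, so the result is Φ(−1.710) = 0.0436, provided events are fully recorded. If only a fraction q of non-starters' events is recorded, the observed rate is r((1 − x) + xq). With q = 0.5 and 20%/5% non-starters the rates are 7.20% and 7.80%, SE = 0.0203, and the error is 0.0225. With the shares reversed it is 0.0785.

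**4. Noninferiority in mITT.** With a true 3-point deficit for DOAC and the first two pairs of shares, false noninferiority is 0.0572 and 0.0714 (half risk in both arms), or 0.0629 and 0.0885 (half risk in usual care only).

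**5. Power price of moving superiority to ITT.** Anchor on the stated power: (1.645 + 0.693) × √(671/668) = 2.344. At 1.710 with no exclusions, Φ(2.344 − 1.710) = 0.737. For the same share x excluded in both arms, mITT power is Φ(2.344√(1 − x) − 1.710) and ITT power, if the excluded contribute no difference, is Φ(2.344(1 − x) − 1.710).

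| x | mITT | ITT |
|---|---|---|
| 5% | 0.717 | 0.697 |
| 10% | 0.696 | 0.655 |
| 20% | 0.650 | 0.566 |

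If every excluded patient took the other class, ITT power is Φ(2.344(1 − x_UC − x_DOAC) − 1.710): 0.638 for 10%/2% and 0.519 for 20%/5%. The mITT figures are 0.712 and 0.682.

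**The case against.** **ITT will be reported anyway.** This is true: all analyses are repeated in ITT, so an ITT superiority result will exist, and sensitivity analyses often carry no override rule. What stands of the concern is that the claim is made without it.

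**Superiority is only a second step.** Also true. The hypotheses in protocol section 2.0 and SAP 2.1 for VTE recurrence are of the not-worse kind, and mITT noninferiority has much the same exposure to selection (step 4). That limits the weight of the point. It does not supply a reason for mITT in the superiority test.

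**The type I error statement is correct.** A reader might infer that the SAP's sentence on maintained error is wrong. It is not. It concerns multiplicity, and testing superiority only after noninferiority needs no alpha split. It does not address selection after randomisation.

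**ITT is not automatically clean.** This stands. Events come from chart abstraction and questionnaires. Missing questionnaires are not violations (protocol 7.0), and patients may withdraw from questionnaires or chart access (protocol 8.8). Protocol 8.9 says that never-starters should complete follow-up, which is not proof that they do. Step 3 shows that unequal capture moves the ITT error in either direction, so no error guarantee can be attached to the change.

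**The size is invented.** The rates, shares and risks are assumed, and the results fall on both sides of nominal. That is accepted: the figures show that the error is uncontrolled, not that it is high.

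**Conclusion.** The point holds as a gap in justification and in the decision rule. Superiority is decided in a set defined after randomisation, for a reason that applies only to noninferiority, while the set that the same reasoning favours for superiority cannot stop the claim.

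Two stronger readings are tempting and unsupported. One is that mITT favours DOAC. The documents give neither the number excluded by arm nor their risk, and the error falls below nominal as readily as it rises above it. Exclusion unrelated to risk, or the same share and relative risk in both arms, leaves it unchanged. The other is that the set was chosen with outcomes by arm in view. The SAP places the data review before the final analysis and does not say whether it was blind to outcomes; silence does not show that it was not.

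The advantage of ITT rests on one assumption: that events are captured equally well in the non-starters of both arms.

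**What to change.** In SAP 3.5.2.1 item 2 and protocol 13.3.1 item 2, replace both sentences of the superiority rule: the one that names the interval and the one that gives the upper-bound criterion. If only the first were changed, the second would still point to the mITT interval. Proposed text:

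> If noninferiority is shown in the mITT population, superiority will be tested in the ITT population of the randomized cohort. DOAC will be declared superior if the upper bound of the ITT confidence interval for the difference, at the confidence level set for the final analysis in 3.5.2.2 [protocol: 13.3.2], is below 0.

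Apply the same population rule to the major-bleeding sequence (SAP 3.6.2 item 1; protocol 13.3.5 item 1).

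This leaves the selection risk in mITT noninferiority where it is. Beside that result, report the ITT noninferiority result and the mITT exclusions by arm, reason and drug received. The 2-week form already asks for reason and drug (protocol 8.5).

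The cost is wording, since the ITT runs are already planned, plus the loss of superiority power in step 5. That loss is small at 5% excluded and material at 20%, more so if the excluded patients took the other class.

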### Per-protocol population

The per-protocol population includes those patients who received a study drug of the assigned treatment group and do not have any major protocol violations.

The randomized per protocol population includes those subjects who received a study drug according to the randomized treatment assignment and do not have any major protocol violations. The preference per protocol population includes those subjects who were not randomized and received a study drug according to the subject's preference and do not have any major protocol violation. The full per protocol population is the sum of the two aforementioned categories.

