**Note about missing forms:**

- If any of the following forms are missing for a participant, then this would constitute a major protocol violation:
  - Eligibility Checklist/Enrollment Form
  - Treatment Status Update Form
  - Medical Record Abstraction Form
  - Change in Enrollment Status/Off-Study Form (as needed)
  - Expedited Serious Adverse Event (SAE) Reporting Form (as/if needed)
- Protocol violations must be filed after a form is missing for greater than 30 days after the data entry window has closed (please refer to Section 7.0 for schedule of assessments).
- If any of the following forms are missing for a participant despite best efforts by Central Study Coordinator and Site Staff to collect from participant, then this does not constitute a major or minor protocol violation:
  - Baseline Study Questionnaire
  - Follow-up Study Questionnaire - 3 months
  - Follow-up Study Questionnaire - 6 months
  - Medication Diary - Month 1 of 6
  - Medication Diary - Month 2 of 6
  - Medication Diary - Month 3 of 6
  - Medication Diary - Month 4 of 6
  - Medication Diary - Month 5 of 6
  - Medication Diary - Month 6 of 6

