## 8.5 Treatment Status Update Form

2-weeks after the participant has been enrolled, the site staff should submit the Treatment Status Update Form via <https://redcap.partners.org>. The Treatment Status Update Form will ask sites to report: (1) whether or not the participant is receiving treatment in accordance with the treatment arm to which s/he was assigned (see next paragraph for more information); (2) if yes, which anticoagulation drug is the participant receiving; (3) if no, why not (e.g., due to insurance non-coverage, patient refusal, transfer of care, receive no anticoagulation therapy, other); (4) if no, which anticoagulation drug is the participant receiving, if any.

If participant is not receiving treatment in accordance with the treatment arm to which s/he was assigned, that is NOT a protocol violation. Please keep this patient ON STUDY.

- Arm 1: Switching between DOACs is allowed
- Arm 2: Switching between LMWH/warfarin is allowed
- Anticoagulation “breaks” and “gaps” are not protocol violations
- Arm 1: Switching to LMWH is discouraged but is not a protocol violation.
- Arm 2: Switching to DOAC is discouraged but is not a protocol violation
- Record abstraction and medication diaries will ascertain these rates

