#### 11.5 Dose Modifications

Dose modifications are allowed, and are not considered protocol violations.

- Skipped or omitted doses are not protocol violations.
- Drug discontinuation is not a protocol violation.
- Delayed or postponed doses are not protocol violations.
- Dose reductions are not protocol violations and should be done at the discretion of the treating clinician.
- Re-escalation of doses is not a protocol violation and should be done at the discretion of the treating clinician.

***When making dose modifications, the guiding principal should be:*** Regardless of treatment arm and/or anticoagulation drug(s) used, treat the patient according to individual institutional guidelines, the best clinical judgment of the responsible physician, and in consultation with the drug's package insert and with national treatment guidelines.

At 3 and 6 months, participants will report their use of treatment, the number of days with no anticoagulant therapy, and the number of days with each type of anticoagulant therapy. Study CRAs will also abstract this information from medical records at 6 months.

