## REPORTING REQUIREMENTS FOR SERIOUS ADVERSE EVENTS

### **For this study, SAE requiring expedited reporting is defined as:**

ALL adverse events that meet the following criteria MUST be reported via the Expedited SAE Reporting Form at <https://redcap.partners.org>:

- 1) All deaths on study require expedited reporting regardless of causality. Attribution to treatment or other cause should be provided.
- 2) Any grade 3, 4, or 5 bleeding or hemorrhaging event.
- 3) Any AEs that result in blood transfusion(s).
- 4) Any thromboembolic event (e.g., VTE, DVT, PE, blood clot, thrombosis, or embolism).
- 5) Edema, dyspnea, stroke, and/or respiratory failure must be reported IF AND ONLY IF related to a thromboembolic event (e.g., VTE, DVT, PE, blood clot, thrombosis, or embolism).
- 6) All other events do NOT need to be reported as expedited SAEs.

If an AE meets the definition of SAE requiring expedited reporting as defined above, the AE must initially be reported via the Expedited SAE Reporting Form at <https://redcap.partners.org>  $\leq$  24 hours of learning of the AE, followed by a complete expedited report via the Expedited SAE Reporting Form at <https://redcap.partners.org>  $\leq$  5 calendar days of the initial 24-hour report.

Serious adverse events that occur more than 30 days after the last administration of study protocol treatment and have an attribution of possible, probable, or definite require reporting as follows:

- If an AE meets the definition of SAE requiring expedited reporting as defined above, the AE must initially be reported via the Expedited SAE Reporting Form at <https://redcap.partners.org>  $\leq$  24 hours of learning of the AE, followed by a complete expedited report via the Expedited SAE Reporting Form at <https://redcap.partners.org>  $\leq$  5 calendar days of the initial 24-hour report.

Treatment expected adverse events include those listed in Section 12.4 Expected Adverse Reactions and in the package insert.

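### The per-protocol set is in effect the modified ITT set minus patients with missing site forms: it adds no check on switching or stopping after the first dose, and it can delete known endpoint events

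*Combined protocol and SAP*

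**What the plan says.** SAP 3.2 sets two conditions for the randomized per-protocol population: the subject "received a study drug according to the randomized treatment assignment and do not have any major protocol violations". It gives no minimum exposure and no list of major violations. The modified ITT population, which is primary, takes randomized subjects who "received at least one dose of the anti-coagulation treatment strategy to which they were assigned".

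The term major violation is given content in one place, the note on missing forms in protocol section 7.0: "If any of the following forms are missing for a participant, then this would constitute a major protocol violation". Five site forms follow: eligibility/enrollment, treatment status update, medical record abstraction, change in enrollment status/off-study, and "Expedited Serious Adverse Event (SAE) Reporting Form (as/if needed". Missing questionnaires and diaries are expressly not violations.

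On treatment, protocol 8.5 says "Arm 1: Switching to LMWH is discouraged but is not a protocol violation", has the matching rule for Arm 2, and says the same of breaks and gaps. Section 11.5 says "Drug discontinuation is not a protocol violation", and sections 11.4 and 11.5 treat interruptions, skipped doses and dose changes alike.

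The triggers for the SAE form (protocol 7.0 and 12.3) include all deaths, "Any grade 3, 4, or 5 bleeding or hemorrhaging event", adverse events leading to transfusion, and "Any thromboembolic event (e.g., VTE, DVT, PE, blood clot, thrombosis, or embolism".

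SAP 3.5.2.3(6) repeats all analyses in the ITT and then the per-protocol population, as sensitivity analyses.

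**The concern.** SAP 3.2 moves the primary analysis from ITT to modified ITT because treatment off assignment could bias the result toward noninferiority, and it reports that a fair number of subjects were affected. The same bias can arise when a patient takes one dose of the assigned strategy and then changes class or stops. A reader would expect the per-protocol analysis to address that. As defined it does not, so agreement between per-protocol and modified ITT is largely built in and could be mistaken for confirmation.

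The exclusions it does make are also a problem. A missing SAE form can occur only in someone who had a reportable event, and those events include the primary endpoint and both components of the major bleeding and death composite in SAP 3.6.2. The event can still be known from the patient questionnaire or the chart abstraction, so the rule can drop a known event together with the patient who had it.

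**Working it through.** The plan gives no figure for this point: no VTE rate by arm, no switching share and no form-loss share. The first step is textual and the rest is illustration.

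**1. The definitions side by side**

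| Patient | Modified ITT | Per-protocol as written |
|---|---|---|
| Never took the assigned strategy | out | out |
| One dose of assigned drug, then the other arm's class to month 6 | in | in |
| Took assigned drug, then stopped all anticoagulation | in | in |
| Recurrence in the chart, SAE form never filed | in | out |
| No event, all forms filed | in | in |

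On the stated rules, the two sets differ only through missing forms.

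**2. Inputs for the illustration**

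- From the documents: margin 3 points on the upper confidence bound (SAP 3.5.2.1); final critical value 1.710 (SAP 3.5.2.2); 668 randomized, or 334 per arm (SAP 2.5). The stated alpha checks: 1 − Φ(1.710) = 0.0436.
- Assumed: control rate 6% and a true DOAC rate of 9%, exactly at the margin, with 334 per arm kept throughout. A control rate of 9% (DOAC 12%) is the alternative.
- SE = √{[p₀(1 − p₀) + p₁(1 − p₁)]/334}. The chance that the upper bound falls below 3% is Φ((0.03 − d)/SE − 1.710), where d = p₁ − p₀. With nothing lost it is 0.044.

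**3. Event patients removed for a missing SAE form**

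If a share m of event patients is dropped, the observed rate is p(1 − m)/(1 − pm). For m = 0.10:

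- 9%: 0.081/0.991 = 8.17%
- 6%: 0.054/0.994 = 5.43%
- d = 2.74 points instead of 3.00
- SE = 1.945 points, and Φ(0.26/1.945 − 1.710) = 0.057

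This is about three DOAC patients (334 × 0.09 × 0.10) and two control patients (334 × 0.06 × 0.10). Other equal shares:

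| Share lost, both arms | d (control 6%) | Chance of bound < 3% | Same chance, control 9% |
|---|---|---|---|
| 5% | 2.87 | 0.050 | 0.049 |
| 10% | 2.74 | 0.057 | 0.054 |
| 20% | 2.47 | 0.077 | 0.069 |
| 30% | 2.20 | 0.106 | 0.090 |

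Unequal loss moves the difference either way. With 10% lost in the DOAC arm only, d = 8.17 − 6.00 = 2.17; in the control arm only, d = 9.00 − 5.43 = 3.57.

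**4. Switching after the first dose, which the set leaves in**

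If switching removes 10%, 20% or 30% of the 3-point excess, d is 2.7, 2.4 or 2.1 points. The chance of a bound below 3% is then 0.059, 0.079 or 0.105 (control 9%: 0.057, 0.073, 0.093). For the 20% case, SE = √[(0.0564 + 0.0769)/334] = 1.998 points, and Φ(0.6/1.998 − 1.710) = 0.079. Per-protocol as written retains these patients and so carries the same dilution as modified ITT.

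**The case against.** Several points on the other side stand.

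- **Crossover from the start is handled.** A reader might infer that the per-protocol set cannot test noninferiority against crossover at all. It does exclude patients who only ever took the other arm's drug, which is the case SAP 3.2 names. Modified ITT already excludes them, so what is missing is a further check after the first dose.
- **The list in section 7.0 is not said to be exhaustive.** Ineligibility, consent failures or a late start might also be treated as major violations. No section says so, and membership would then rest on judgement not fixed in the SAP, which itself needs repair.
- **A diluted difference inside 3 points does not deliver noninferiority.** Suppose DOAC is truly 4 points worse and each arm spends 15% or 20% of follow-up on the other arm's drugs. The expected difference is 4 × (1 − 0.30) = 2.8 or 4 × (1 − 0.40) = 2.4 points. It is tempting to say the trial would then pass. The rule uses the upper bound. The stated 6.1% interval length implies SE = 6.1/(2 × 1.645) = 1.85 points, so the chance of passing is Φ(0.2/1.85 − 1.710), about 5%, or Φ(0.6/1.85 − 1.710), about 8%.
- **The trial compares management strategies.** Keeping switchers fits that question, and switching after a recurrence cannot dilute a time-to-first-recurrence analysis. This supports modified ITT or ITT as primary. It does not make a per-protocol set that ignores treatment informative.
- **Some of this is examined elsewhere.** SAP 3.7 reports persistence on any and on assigned therapy, and SAP 3.9.4 has persistence subgroups. Those subgroups are exploratory and, as worded, count days on anticoagulant therapy rather than on the assigned class, so they address stopping but not switching.

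**Conclusion.** The point holds in a limited form. On the stated rules, the randomized per-protocol set is in effect modified ITT less patients with missing site forms. It adds nothing on switching or stopping after the first dose, and through the SAE form it can selectively remove known recurrences, major bleeds and deaths. Equal loss in both arms shrinks a true excess toward noninferiority: 3.00 to 2.74 points at an assumed 10% loss with rates of 9% and 6%. Unequal loss could push either way. The rates, loss shares and switching shares are all assumptions. The actual effect could be negligible if nearly all SAE forms were filed, and a violation is filed only once a form is more than 30 days past its window.

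A reader might also infer that the primary conclusion is compromised. The documents do not support that: per-protocol is a sensitivity analysis with no decision rule attached, and the primary result rests on modified ITT. This is a change that should be made, not one on which the trial's validity turns.

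**What to change.** In SAP 3.2, list the per-protocol exclusions explicitly. Remove missing forms as grounds for exclusion, at minimum the SAE form and the off-study form, which is also tied to deaths and to coming off treatment. Define the set by treatment received, for example starting the assigned strategy within the 14 days the protocol already sets.

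In SAP 3.5.2.3(6), add a sensitivity analysis that censors follow-up at the first switch to the other arm's class or at the first gap off all anticoagulation longer than a length fixed before the analysis. Keep death as a competing event and read the upper bound against the same 3%.

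The cost is SAP wording and one added analysis, using drug data already collected in diaries, questionnaires and record abstraction. The interval will be wider, and censoring at a switch may be informative. Censoring weights could reduce that but are optional. They need time-varying predictors and complete switch dates, while follow-up laboratory tests are not required and missing diaries are tolerated. The weights already in SAP 3.5.2.3(5) serve a different model and would not carry over unchanged. Report the number of patients censored by arm and reason beside the result.
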